5.6.9. Sampling

Refer to the Module on Biospecimen Management in the SPM for detailed instructions for the collection, handling and processing of the samples.

5.6.9.1. Blood sampling for antibody determination

Blood samples will be taken at Visit 1 and Visit 2 as specified in Section 5.5, List of Study Procedures.

- A volume of approximately 5 ml of whole blood (to provide approximately 1.7 ml of serum) should be drawn from all subjects at the pre-booster and post-booster timepoint (Visit 1 and Visit 2). After centrifugation, serum samples should be kept at –20°C or below until shipment.

Refer to the Module on Biospecimen Management in the SPM for detailed instructions for the collection, handling and processing of the samples.

5.6.10. Study Vaccine administration

- After completing all prerequisite procedures prior to vaccination, the study vaccine will be administered intramuscularly in the deltoid muscle of the non-dominant arm (refer to Section 6.3 for detailed description of the vaccine administration procedure). If the investigator or delegate determines that the subject's health on the day of administration temporarily precludes vaccine administration, the visit will be rescheduled.
- The subjects will be observed closely for at least 30 minutes following the administration of the vaccine, with appropriate medical treatment readily available in case of anaphylaxis.

5.6.11. Check and record concomitant medication/vaccination and intercurrent medical conditions

Concomitant medication/vaccination must be checked and recorded in the eCRF as described in Section 6.7.

Intercurrent medical conditions must be checked and recorded in the eCRF as described in Section 6.8.

5.6.12. Distribution of diary cards and recording of AEs, SAEs and pregnancies

- Refer to Section 8.3 for procedures for the investigator or delegate to record AEs, SAEs, and pregnancies. Refer to Section 8.4 for guidelines and how to report SAE, and pregnancy reports to GSK Biologicals.
- The subjects/subjects' parent(s)/adoptive parent (s) will be instructed to contact the investigator or delegate immediately should they/the subjects manifest any signs or symptoms they perceive as serious.
- At Visit 1, diary cards will be provided to the subject/subject's parent(s)/adoptive parent(s). The subject/subject's parent(s)/adoptive parent(s) will record body (preferably axillary) temperature and any solicited local/general AEs (i.e. on the day

of vaccination and during the next three days) or any unsolicited AEs (i.e. on the day of vaccination and during the next 30 days) occurring after vaccination. The subject/subject's parent(s)/adoptive parent(s) will be instructed to return the completed diary card to the investigator or delegate at the next study visit.

- Note: Diary cards can be filled in by a minor subject under the supervision of the subject's parent(s)/adoptive parent(s) provided that the minor has the competency to assess and report the information to be provided in the diary card. The ultimate accountability for the completion of the diary cards remains with the subject's parent(s)/adoptive parent(s). The investigator or delegate should discuss this accountability with the subject's parent(s)/adoptive parent(s).
- Collect and verify completed diary cards during discussion with the subject/subject's parent(s)/adoptive parent(s) on Visit 2.
 - Note: If the diary card has been filled in by a minor subject, the investigator or delegate should verify the reported information during a discussion with the minor subject preferably in the presence of his/her parent(s)/adoptive parent(s).
- After vaccination, if the subjects or the subject's parents/adoptive parents observe any large injection site reaction (for subjects <6 years of age defined as a swelling with a diameter of >50 mm and for subjects ≥6 years of age swelling with a diameter of >100 mm, noticeable diffuse swelling or noticeable increase in limb circumference) during the 4-day follow-up (Day 1-4) period, they will be asked to contact study personnel and to visit the investigator's office for evaluation as soon as possible. The investigator or delegate will record detailed information describing the AE on a specific large injection site reaction screen in the eCRF.

5.6.13. Return of diary card and diary card transcription

- Any unreturned diary cards will be sought from the subject/subject's parent(s)/adoptive parent(s) through telephone call(s) or any other convenient procedure. The investigator or delegate will transcribe the collected information into the eCRF in English.

5.6.14. Recording of AEs, SAEs and pregnancies

- Refer to Section 8.3 for procedures for the investigator or delegate to record AEs, SAEs, pregnancies. Refer to Section 8.4 for guidelines and how to report SAE and pregnancy reports to GSK Biologicals.
- The subject/subjects' parent(s)/adoptive parent(s) will be instructed to contact the investigator immediately should they/the subjects manifest any signs or symptoms they perceive as serious.

5.6.15. Study conclusion

The investigator will:

- review data collected to ensure accuracy and completeness
- complete the Study Conclusion screen in the eCRF.

5.7. Biological sample handling and analysis

Please refer to the SPM for details on Biospecimen Management (handling, storage and shipment).

Samples will not be labelled with information that directly identifies the subject but will be coded with the identification number for the subject (subject number).

- Collected samples will be used for protocol mandated research and purposes related to the improvement, development and quality assurance of the laboratory tests described in this protocol. This may include the management of the quality of these tests, the maintenance or improvement of these tests, the development of new test methods, as well as making sure that new tests are comparable to previous methods and work reliably.
- It is also possible that future findings may make it desirable to use the samples acquired in this study for future research, not described in this protocol. Therefore, all subjects will be asked to give a specific consent to allow GSK or a contracted partner to use the samples for future research. Future research will be subject to the laws and regulations in Russia and will only be performed once an IEC or IRB has approved this research.

Information on further investigations and their rationale can be obtained from GSK Biologicals.

Any sample testing will be done in line with the consent of the individual subject/subject's parent(s)/adoptive parent(s).

Refer also to the [Investigator Agreement](#), where it is noted that the investigator cannot perform any other biological assays except those described in the protocol or its amendment(s).

If additional testing is performed, the marker priority ranking given in Section [5.7.4](#) may be changed.

Collected samples will be stored for a maximum of 20 years (counting from when the last subject performed the last study visit), unless local rules, regulations or guidelines require different timeframes or different procedures, which will then be in line with the subject consent. These extra requirements need to be communicated formally to and discussed and agreed with GSK Biologicals.

5.7.1. Use of specified study materials

When materials are provided by GSK Biologicals, it is MANDATORY that all clinical samples (including serum samples) be collected and stored exclusively using those materials in the appropriate manner. The use of other materials could result in the exclusion of the subject from the per protocol (PP) analysis (See Section 10.4 for the definition of cohorts to be analysed). The investigator must ensure that his/her personnel and the laboratory(ies) under his/her supervision comply with this requirement. However, when GSK Biologicals does not provide material for collecting and storing clinical samples, appropriate materials from the investigator's site must be used. Refer to the Module on Clinical Trial Supplies in the SPM.

5.7.2. Biological samples

The biological samples required for this study have been presented in [Table 7](#).

Table 7 Biological samples

Sample type	Quantity	Unit	Timepoint
Blood	Approximately 5	ml	Pre-Bst ¹ and Post-Bst ²

¹ Pre-Bst: Before the administration of study vaccine.

² Post-Bst: one month after the administration of study vaccine.

5.7.3. Laboratory assays

Please refer to [APPENDIX A](#) for the address of the clinical laboratories used for sample analysis.

All serology will be determined in GSK Biologicals' laboratories or in a laboratory designated by GSK using standardized and validated procedures with adequate controls.

Refer to [Table 8](#) for the assays used in antibody determination.

Table 8 Humoral Immunity (Antibody determination)

System	Component	Method	Kit/Manufacturer	Unit	Cut-off†	Laboratory*
Serum	Corynebacterium diphtheriae . Diphtheria Toxoid Ab.IgG	ELI	NA	IU/ml	0.057	GSK Biologicals or designated laboratory
Serum	Corynebacterium diphtheriae . Diphtheria Toxoid Ab	NEU assay on Vero cells**	NA	IU/ml	0.004	GSK Biologicals or designated laboratory
Serum	Clostridium tetani . Tetanus Toxoid Ab.IgG	ELI	NA	IU/ml	0.043	GSK Biologicals or designated laboratory
Serum	Bordetella pertussis . Pertussis Toxin Ab.IgG	ELI	NA	IU/ml	2.693	GSK Biologicals or designated laboratory
Serum	Bordetella pertussis . Filamentous Hemagglutinin Ab.IgG	ELI	NA	IU/ml	2.046	GSK Biologicals or designated laboratory
Serum	Bordetella pertussis . Pertactin Ab.IgG	ELI	NA	IU/ml	2.187	GSK Biologicals or designated laboratory

ELI: ELISA

NEU: Neutralisation assay

NA: Not Applicable

IU/ml: International Units per millilitre

†**ELISA's** for diphtheria, tetanus and pertussis were re-developed and re-validated as per most recent CBER recommendations (Guidance for Industry "Bioanalytical Method Validation" from September 2013). The new assay cut-offs that apply are listed in the table. **The neutralisation assay for Diphtheria is still under re-development and the assay cut-off might be subject to change during the course of the study. In this case, it will be documented in the clinical study report. (Amended 31 October 2017)**

*GSK Biologicals laboratory refers to the Clinical Laboratory Sciences (CLS) in Rixensart, Belgium and Wavre, Belgium.

**Test on Vero-cells will be performed on pre- and post-vaccination samples with concentrations <0.1 IU/ml by ELISA.

The GSK Biologicals' clinical laboratories have established a Quality System supported by procedures. The activities of GSK Biologicals' clinical laboratories are audited regularly for quality assessment by an internal (sponsor-dependent) but laboratory-independent Quality Department.

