5.7.5. Immunological correlates of protection

The following cut-offs are accepted as immunological correlates of protection:

- Specific antibodies against diphtheria toxoid (anti-diphtheria) and tetanus toxoid (anti-tetanus) will be measured by enzyme-linked immunosorbent assay (ELISA). The newly validated assay cut-off for anti-diphtheria is currently set at 0.057 IU/ml and for anti-tetanus at 0.043 IU/ml. For both serology a threshold of 0.1 IU/ml provides a conservative estimate of the percentage of subjects deemed to be protected [Camargo, 1984; Melville-Smith, 1983].
- The cut-off of the Vero-cell neutralisation assay (performed for pre- and post-vaccination serum samples when ELISA anti-diphtheria antibody concentrations are <0.1 IU/ml) is 0.004 IU/ml. Antibody concentrations ≥ 0.01 IU/ml are considered as protective [WHO, 1994]. **Both the ELISA test (antibody concentrations ≥ 0.1 IU/ml) and Vero-cell test (antibody concentration ≥ 0.01 IU/ml) will define the seroprotection status for the primary endpoint. (Amended 31 October 2017)**
- No serological correlate of protection is defined for the immune response to pertussis antigens. Antibodies against the pertussis components PT, FHA and PRN will be measured by ELISA technique. The newly validated assay cut-off for anti-PT is 2.693 IU/ml, for anti-FHA is 2.046 IU/ml and for anti-PRN is 2.187 IU/ml. Subjects with antibody concentration below this cut-off will be considered seronegative.

The immunological assay results will be communicated to the investigator as soon as they become available.

The investigator is encouraged to share the immunological assay results for non-responders with the study subjects/subjects' parent(s)/adoptive parent(s).

For the subjects identified as non-responders, it remains the responsibility of the investigator in charge of the subject's clinical management to determine the medical need for re-vaccination and to re-vaccinate the subjects as per local/regional practices.

Non-responders are defined as:

- Antibody concentrations <0.01 IU/ml post-booster for diphtheria antigen by Vero-cell neutralisation assay and,
- Antibody concentrations <0.1 IU/ml post-booster for tetanus antigen by ELISA assay.

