10. STATISTICAL METHODS

10.1. Primary endpoint

- Immunogenicity with respect to components of the study vaccine.
 - Anti-diphtheria* and anti-tetanus seroprotection status, one month after vaccination.
 - Anti-PT, anti-FHA and anti-PRN seropositivity status, one month after vaccination.

*Sera with ELISA concentrations <0.1 IU/ml will be tested for neutralising antibodies using a Vero-cell neutralisation assay.

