N = number of subjects included in the PP cohort for immunogenicity

D and T: % of subjects with antibody concentration ≥0.1 IU/ml; PT, FHA and PRN: % of subjects with antibody concentration ≥5 EL.U/ml.

VR= Vaccine response:

Booster responses to the diphtheria and tetanus antigens, defined as:

For subjects with pre-vaccination concentration below seroprotection cut-off (<0.1 IU/ml): antibody concentrations at least ≥0.4 IU/ml one month after vaccination.

For subjects with pre-vaccination concentration equal or above seroprotection cut-off (≥0.1 IU/ml): an increase in antibody concentrations of at least four times the pre-vaccination concentration one month after vaccination.

Booster response to the PT, FHA and PRN antigens, defined as:

For initially seronegative subjects (pre-vaccination concentration below cut-off: <5 EL.U/ml): antibody concentrations at least four times the cut-off (post-vaccination concentration ≥20 EL.U/ml)

For initially seropositive subjects with pre-vaccination concentration ≥5 EL.U/ml and <20 EL.U/ml: an increase in antibody concentrations of at least four times the pre-vaccination concentration.

For initially seropositive subjects with pre-vaccination concentration ≥20 EL.U/ml: an increase in antibody concentrations of at least two times the pre-vaccination concentration.

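### Section 5.7.3 lets the Vero-cell assay behind primary diphtheria seroprotection change during the study with only a note in the report, so one primary rate may pool sera from different assay versions

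*Protocol*

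**What the plan says.** Protocol 10.1 names anti-diphtheria seroprotection one month after vaccination as a primary endpoint, with the footnote "Sera with ELISA concentrations <0.1 IU/ml will be tested for neutralising antibodies using a Vero-cell neutralisation assay". Section 5.7.5 states that the ELISA result at 0.1 IU/ml or above and the "Vero-cell test (antibody concentration ≥ 0.01 IU/ml") together "will define the seroprotection status for the primary endpoint". Under Table 8 the rule covers both timepoints: "Test on Vero-cells will be performed on pre- and post-vaccination samples with concentrations <0.1 IU/ml by ELISA".

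Section 5.7.3 opens by saying that all serology is done "using standardized and validated procedures with adequate controls". The footnote to Table 8 then reports that the ELISAs were re-developed and re-validated, but adds: "The neutralisation assay for Diphtheria is still under re-development and the assay cut-off might be subject to change during the course of the study". On what follows from a change, it says only: "In this case, it will be documented in the clinical study report".

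The current Vero-cell assay cut-off is 0.004 IU/ml (Table 8 and 5.7.5). The Vero-cell protection threshold is 0.01 IU/ml in 5.7.5 but 0.1 IU/ml in 10.5.

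**The concern.** An assay that helps decide a primary endpoint should be the same assay for every subject. Here the protocol expressly allows it to change while the study runs. It does not ask for one version, a retest, bridging or an amendment before the change. Section 5.7.5 sends results to investigators as they become available, which is compatible with testing in several runs.

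If two versions are used, a serum near the threshold could be called protected or not because of the version that measured it. The study has a single group and no comparator, so nothing in the data would separate such a shift from the vaccine response. Pre-booster sera are tested too, so the pre-vaccination rate reported under 10.7 is exposed in the same way. A new cut-off above the threshold would also leave sera between the two unclassifiable, both for the primary endpoint and for the non-responder definition in 5.7.5.

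**Working it through.** **1. The plan's own figures.** 100 evaluable per stratum at 10% drop-out: 100/0.9 = 111.1, rounded up to 112; 4 × 112 = 448, as stated. Exact (Clopper-Pearson) 95% intervals for Table 18: 364/400 gives 87.8 to 93.6, 385/400 gives 93.9 to 97.9, and 398/400 gives 98.2 to 99.9. All match.

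**2. When a cut-off change alone matters.** The value said to be changeable is the assay cut-off, 0.004 IU/ml. Status is decided at the protection threshold.
- Threshold 0.01 (5.7.5): the cut-off must rise by more than 0.01/0.004 = 2.5-fold before any serum is affected.
- Threshold 0.1 (10.5): it must rise by more than 0.1/0.004 = 25-fold.

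Below that, status changes only if re-development moves the measured concentrations across the threshold.

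**3. How many post-booster sera rest on Vero-cell.** The inputs are the Table 22 diphtheria rates, described as "D and T: % of subjects with antibody concentration ≥0.1 IU/ml". The assay is not named, so treating these as ELISA-only rates is an assumption. The rows below 100% are:

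| Reference group | N | Rate (%) | Expected sera below 0.1 IU/ml |
|---|---|---|---|
| Australia, under 40 | 214 | 96.2 | 214 × 0.038 = 8.13 |
| Australia, 40 and over | 214 | 91.1 | 214 × 0.089 = 19.05 |
| Belgium, 10-18 | 218 | 99.5 | 218 × 0.005 = 1.09 |
| Belgium, 40 and over | 139 | 99.3 | 139 × 0.007 = 0.97 |

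The sum is 29.24. Total N over all eight rows is 319 + 214 + 214 + 447 + 218 + 172 + 139 + 60 = 1,783. The weighted shortfall is 29.24/1,783 = 1.64%, and 0.0164 × 400 = 6.6, so about 7 of 400.

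- One stratum at the lowest rate: 0.089 × 100 = 8.9, about 9 of 100.
- Both adult strata at the lowest rate, with the two younger strata at 99.5 to 100%: 2 × 8.9 = 17.8, plus 0 to 1, so about 18 to 19 of 400.
- All four strata at the lowest rate: 0.089 × 400 = 35.6, about 36 of 400.

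**4. The outer limits.** These run from Vero-cell calling none of those sera protected to calling all of them protected:
- 7 of 400: from 393/400 = 98.25% to 100%.
- 9 of 100: from 91% (83.6 to 95.8) to 100% (96.4 to 100).
- 36 of 400: from 364/400 = 91.0% (87.8 to 93.6) to 100% (99.1 to 100).

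These spans are the whole contribution of the assay. A change of version would reclassify only the sera close enough to the threshold to cross it, which is some fraction of each count. The protocol gives no data from which to estimate that fraction.

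**The case against.** The strongest reply is that the protocol nowhere says results from two versions will be combined. Sera are frozen until shipment (5.6.9.1). The glossary allows up to eight months after the last visit for testing to finish, and there is one analysis on final data (10.10). Any change might therefore come before the first serum is run. That is fair: pooling is left open, not planned. It does not answer the point that the text permits it and sets no condition.

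Several stronger readings are tempting, and the documents do not support them.
- A reader might infer that any cut-off change moves the primary rate. Step 2 shows it does not.
- A reader might take 91% to 100% as the effect of a version change. It is the effect of the whole assay, at the worst reference row applied to all ages.
- A reader might conclude that the current Vero-cell version is unvalidated. The footnote says it is being re-developed, and the ELISAs show that re-development can apply to an established assay. The general statement on validated procedures still binds.
- A reader might say the composite rate cannot be set against the reference rates. Table 22 does not name its assay, and no formal comparison is planned.

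Section 10.10 also requires deviations from the statistical plan to be described and justified. That adds a duty to explain, but still after the fact. The study is descriptive (10.9), so type I error and power are not at issue. Nor will every serum below 0.1 IU/ml necessarily be tested, since Vero-cell ranks last in Table 9 when volume is short.

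**Conclusion.** The point holds as a cheap improvement to the plan. The protocol itself fixes how a change in a primary-endpoint assay is handled, and a note in the report is too little. The harm is to the interpretability of one primary rate, and it is probably small: about 7 of 400 sera depend on Vero-cell on the weighted reference average, about 9 of 100 in a stratum like the lowest reference group, and 36 of 400 only in the extreme case. A version change would move only part of these. The counts assume that the Table 22 rates are ELISA-only and that the Russian strata resemble the reference groups.

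The threshold conflict stands on its own. Sections 5.7.5 and 10.5 give Vero-cell values ten-fold apart for the same endpoint. Until they are reconciled, the primary diphtheria definition is not settled, whichever assay version is used.

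**What to change.** - **5.7.3:** state that all pre- and post-booster Vero-cell sera are tested with one validated assay version, with its cut-off fixed before the first study serum is run. Any serum already run on another version is retested or bridged. Waiting for the fixed version is safer than relying on retests, because each draw yields only about 1.7 ml of serum.
- **5.7.5 and 10.5:** reconcile the Vero-cell protection threshold. The sponsor should also specify in advance how sera are classified if the final assay cut-off exceeds that threshold. The same value feeds the non-responder definition, so this review proposes no threshold.
- **10.7:** report the ELISA-only diphtheria rate (0.1 IU/ml or above) with its exact 95% CI beside the composite, so that the reader sees how much rests on Vero-cell.

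The cost is laboratory scheduling, possibly later individual results for investigators, perhaps a few retests, and one extra table row.

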5.7.4. Biological samples evaluation

5.7.4.1. Immunological read-outs

In case of insufficient blood sample volume to perform assays for all antibodies, the samples will be analysed according to priority ranking provided in [Table 9](#).

Table 9 Immunological read-outs

Blood sampling timepoint		No. of subjects	Component	Components priority rank
Type of contact and timepoint	Sampling timepoint			
Visit 1 (Day 1)	Pre-Bst ¹	All	PT, FHA, PRN,	1
			Diphtheria (ELISA), Tetanus	2
			Diphtheria (Vero-cell*)	3
Visit 2 (Day 31)	Post-Bst ¹	All	PT, FHA, PRN,	1
			Diphtheria (ELISA), Tetanus	2
			Diphtheria (Vero-cell*)	3

¹Pre-Bst: Before the administration of study vaccine; Post-Bst: one month after the administration of study vaccine.

* Test on Vero-cells will be performed on pre- and post-vaccination samples with concentrations <0.1 IU/ml by ELISA.

5.7.5. Immunological correlates of protection

The following cut-offs are accepted as immunological correlates of protection:

- Specific antibodies against diphtheria toxoid (anti-diphtheria) and tetanus toxoid (anti-tetanus) will be measured by enzyme-linked immunosorbent assay (ELISA). The newly validated assay cut-off for anti-diphtheria is currently set at 0.057 IU/ml and for anti-tetanus at 0.043 IU/ml. For both serology a threshold of 0.1 IU/ml provides a conservative estimate of the percentage of subjects deemed to be protected [Camargo, 1984; Melville-Smith, 1983].
- The cut-off of the Vero-cell neutralisation assay (performed for pre- and post-vaccination serum samples when ELISA anti-diphtheria antibody concentrations are <0.1 IU/ml) is 0.004 IU/ml. Antibody concentrations ≥ 0.01 IU/ml are considered as protective [WHO, 1994]. **Both the ELISA test (antibody concentrations ≥ 0.1 IU/ml) and Vero-cell test (antibody concentration ≥ 0.01 IU/ml) will define the seroprotection status for the primary endpoint. (Amended 31 October 2017)**
- No serological correlate of protection is defined for the immune response to pertussis antigens. Antibodies against the pertussis components PT, FHA and PRN will be measured by ELISA technique. The newly validated assay cut-off for anti-PT is 2.693 IU/ml, for anti-FHA is 2.046 IU/ml and for anti-PRN is 2.187 IU/ml. Subjects with antibody concentration below this cut-off will be considered seronegative.

The immunological assay results will be communicated to the investigator as soon as they become available.

The investigator is encouraged to share the immunological assay results for non-responders with the study subjects/subjects' parent(s)/adoptive parent(s).

For the subjects identified as non-responders, it remains the responsibility of the investigator in charge of the subject's clinical management to determine the medical need for re-vaccination and to re-vaccinate the subjects as per local/regional practices.

Non-responders are defined as:

- Antibody concentrations <0.01 IU/ml post-booster for diphtheria antigen by Vero-cell neutralisation assay and,
- Antibody concentrations <0.1 IU/ml post-booster for tetanus antigen by ELISA assay.

